- Coverage by LA PrEP will be determined based on the duration of medication from injection date forward. The number of days of coverage per injection were derived from the CAB LA PrEP USPI label.¹⁴
 - 1st injection: coverage = 37 days (30 days of coverage + 7-day injection window)
 - Subsequent injections: coverage = 67 days (60 days of coverage + 7-day injection window)
 - Each calendar day will only be counted once, even if there is an overlap between coverage from the prior injection and date of the next injection.

$$\% \text{ coverage} = \frac{\sum \min(\text{coverage, days between injections})}{\text{Number of FU days}} \times 100\%$$

HIV testing & STI screening

- HIV testing
 - Assessed within 14 days before PrEP start and over the first 12 months after PrEP start
 - Frequency and rate (per 100 person years) of HIV tests over 12-month period
 - Type of HIV tests (RNA [quantitative, qualitative], antigen/antibody, rapid screen)
 - Timing of HIV tests as recommended by PrEP clinical guidelines⁷
 - Oral PrEP: on-schedule testing defined as receiving an HIV test ≤14 days before/at start, and 3 months (76-104 days) after each test
 - LA PrEP: on-schedule testing defined as receiving an HIV test ≤14 days before/at first injection, and ±14 days of each subsequent injection
 - HIV testing practices (type, frequency) by type of healthcare provider (MD or DO, physician associate, nurse practitioner, other/unknown)
 - HIV testing practices (type, frequency) by clinic type (healthcare center, wellness center, other)
- STI screening
 - Assessed within 14 days before PrEP start and over the first 12 months after PrEP start
 - Frequency and rate (per 100 person years) of STI testing events (testing for multiple STIs on the same day will count as 1 testing event)
 - Type of other STI tests
 - Syphilis
 - Gonorrhea
 - Chlamydia
 - Chancroid
 - Lymphogranuloma venereum

- Mycoplasma genitalium
- Hepatitis B virus (HBV)
- Hepatitis C virus (HCV)
- HSV-2
- Trichomoniasis
- HPV and/or genital warts
- Timing of STI tests as recommended by PrEP clinical guidelines⁷
 - Testing 3 months (76-104 days) after last test
 - Testing 6 months (168-196 days) after last test
 - Testing 12 months (351-379 days) after last test
- STI screening practices (type, frequency) by type of healthcare provider (MD or DO, physician associate, nurse practitioner, other/unknown)
- STI screening practices (type, frequency) by clinic type (healthcare center, wellness center, other)

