Through study end		
HIV diagnosis, n (%)		
Months from start of PrEP type to HIV diagnosis, median (IQR)		
Negative HIV test within 2 weeks before/on start of PrEP type, n (%)		

^a Incident HIV is only counted for the PrEP type used at the time of diagnosis

Table 10 Incidence rate of HIV^a within 12 months of index and through study end among PrEP users

	Oral PrEP N=	CAB LA PrEP N=
Within 12 months of index		
HIV diagnosis, n (%)		
Person-years of follow-up		
IR per 100 py (95% CI)		
Through study end		
HIV diagnosis, n (%)		
Person-years of follow-up		
IR per 100 py (95% CI)		

^a Incident HIV is only counted for the PrEP type used at the time of diagnosis

Table 11. Oral PrEP coverage within 12 months of index among **oral** PrEP users

	Oral PrEP N=
Mean # pills prescribed (SD)	
Median # of pills prescribed (IQR)	
Mean days of follow-up on oral PrEP ^a (SD)	
Median days of follow-up on oral PrEP ^a (IQR)	
Mean % access (total pills prescribed/days of follow-up) (SD)	
Median % access (total pills prescribed/days of follow-up) (IQR)	

^a If index PrEP is oral: shortest of (a) days from index to first CAB LA injection or (b) 12 months after index; if index PrEP is CAB LA injections: shortest of (a) days from start of switch to oral PrEP to study end or (b) 12 months after index

Table 12. CAB LA PrEP coverage within 12 months of index among CAB LA PrEP users

	CAB LA PrEP N=
Mean days covered ^a (SD)	
Median days covered ^a (IQR)	
Mean days of follow-up on CAB LA PrEP ^b (SD)	
Median days of follow-up on CAB LA PrEP ^b (IQR)	
Mean % coverage (days covered/days of follow-up) (SD)	
Median % coverage (days covered/days of follow-up) (IQR)	

^b Total days between injections, up to 37 days between the first 2 injections or up to 67 days between subsequent injections

^a If index PrEP is oral: shortest of (a) days from index to first CAB LA injection or (b) 12 months after index; if index PrEP is CAB LA injections: shortest of (a) days from first CAB LA injection to study end or (b) 12 months after index

Table 13. Incidence rate of HIV testing events within 12 months of index among PrEP users^a

	Oral PrEP N=	CAB LA PrEP N=
Total # HIV testing events within 12 months of index, n		
Person-years of follow-up		
IR per 100 py (95% CI)		

^a HIV testing events are only counted for the PrEP type used at the time of diagnosis

Table 14. Frequency and type of HIV testing among PrEP users^a

	Oral PrEP N=	CAB LA PrEP N=

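### Table 12 divides switchers' CAB LA coverage by their time on oral PrEP, and its footnote drops the last injection that Section 7.3.2 credits

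*Protocol*

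**What the plan says.** Protocol Section 7.3.2 defines LA PrEP coverage as the share of follow-up days covered by CAB LA. Its text reads: "Coverage by LA PrEP will be determined based on the duration of medication from injection date forward". It assigns 37 days to the first injection and 67 to each later one, and counts no calendar day twice. Its formula sums the smaller of coverage and days between injections, then divides by follow-up days. Follow-up ends at death, study end, loss to follow-up or 12 months after index. No start or end is given for people who change PrEP type.

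Annex 1, Table 12 puts this into a table shell. One footnote defines days covered: "Total days between injections, up to 37 days between the first 2 injections or up to 67 days between subsequent injections". The other defines the row "Mean days of follow-up on CAB LA PrEP" in two parts:
- People who start on oral PrEP: "If index PrEP is oral: shortest of (a) days from index to first CAB LA injection or (b) 12 months after index".
- People who start on CAB LA: "if index PrEP is CAB LA injections: shortest of (a) days from first CAB LA injection to study end or (b) 12 months after index".

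The oral-index clause is identical to the one under Table 11, where it measures time on oral PrEP. Section 7.7.1.1 allows people who used both types to count in both groups. The opening of Annex 1 says the shells will be reused for Analysis #2 with only the study periods updated.

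**The concern.** For someone who starts on oral PrEP and later moves to CAB LA, the quoted denominator ends on the day CAB LA begins, while the numerator starts on that day. The two share no follow-up time, so the ratio is not a proportion of days and has no upper limit of 100%.

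For everyone, a numerator made only of gaps between injections gives nothing for the final injection. The proportional loss is greatest for people with one or two injections, whom a coverage measure most needs to describe correctly.

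For a CAB LA index, days after a move to oral PrEP stay in the CAB LA denominator, although Table 11 starts counting oral follow-up at that same move.

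CAB LA coverage is half of Objective 4, so these definitions determine a main result of the study.

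**Working it through.** Table 12 is an empty shell, so there is no stated coverage figure to reproduce. The windows add up as stated: 30 + 7 = 37 and 60 + 7 = 67.

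**Inputs.** Caps of 37 and 67 days (Section 7.3.2 and the Table 12 footnote). Assumed for illustration: a 365-day window, no censoring, injections at day s, s + 30 and every 60 days after that. These calendars test the formula and express no view on dosing.

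**Formulas.**
- Footnote numerator: sum of min(37 or 67, days to next injection), with no term for the last injection.
- Section 7.3.2 text: the same sum, plus min(37 or 67, days to end of follow-up) for the last injection.
- Footnote denominator, oral index: s.
- CAB LA time within the window: 365 − s.

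**1. Oral-index switchers, on-time injections**

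| First injection (day s) | Table 12 as written | Covered days / CAB LA time |
|---|---|---|
| 60 | 270/60 = 450% | 305/305 = 100% |
| 90 | 270/90 = 300% | 275/275 = 100% |
| 180 | 150/180 = 83% | 185/185 = 100% |
| 300 | 30/300 = 10% | 65/65 = 100% |

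For s = 90, the injections fall on days 90, 120, 180, 240, 300 and 360. The gaps are 30 + 4 × 60 = 270, and the last injection adds 365 − 360 = 5.

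Section 7.3.2 does not repair this. If its follow-up is taken to start at index, the fully covered day-180 switcher scores 185/365 = 51%.

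**2. Last injection, CAB LA index**

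| Injections | Footnote | Section 7.3.2 text |
|---|---|---|
| Day 0 only | 0/365 = 0% | 37/365 = 10.1% |
| Days 0, 30 | 30/365 = 8.2% | (30 + 67)/365 = 97/365 = 26.6% |
| Days 0, 30, 90, 150, 210, 270, 330 | 330/365 = 90.4% | (330 + 35)/365 = 100% |

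The formula in Section 7.3.2 falls between the two: with no next injection, its second term is undefined.

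**3. CAB LA index, later move to oral.** Take injections at days 0 and 30 and oral PrEP from day 97. Even with the last injection credited, Table 12 gives 97/365 = 26.6%; ending CAB LA follow-up at the move gives 97/97 = 100%. The remaining 365 − 97 = 268 days enter the denominators of both Table 11 and Table 12. Table 12 also leaves out death and loss to follow-up, which Section 7.3.2 lists.

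**4. Footnote markers.** The days-covered rows carry marker a, which is the follow-up definition. The follow-up rows carry marker b, which is the days-covered definition. Sections 1 to 3 above match each footnote to the row its wording fits. Taken strictly by marker, the ratio inverts: the on-time year becomes 365/330 = 111%, and a single injection divides by zero.

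**5. How many people.** Section 7.5 gives 384 starting on CAB LA, 292 switching to it later, and 767 in total. But 384 + 292 = 676. Switchers are therefore 292/767 = 38% or 292/676 = 43%.

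**The case against.** The best defence is that Section 7.3.2 already gives the intended rule. Its text credits every injection from its date with no exception for the last, and the minimum in the formula sits directly under the rule against double counting, so it can be read as handling overlap only. On that reading only the annex footnote loses the last injection, and a SAP, which is not at hand, could settle the final interval. The swapped markers and the clause shared with Table 11 also suggest a copying slip in an empty shell rather than a chosen analysis.

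Much of this stands. A reader might infer that the protocol as a whole gives no credit after the last injection; the Section 7.3.2 text says otherwise, so this is a conflict to reconcile. A reader might also expect values above 100% from crediting the last injection in full (330 + 67 = 397, and 397/365 = 109%). That requires counting days after follow-up ends, which a proportion of follow-up days does not do.

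The defence does not reach the oral-index denominator. It contradicts its own row label, and Section 7.3.2 has no rule for switchers to put in its place. Since the protocol itself fixes this wording, it is not detail left for the SAP.

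**Conclusion.** The point holds, and Table 12 should not be programmed as written. The oral-index denominator is an error: on-time switchers score anywhere from 10% to 450% in the cases shown, when all are fully covered from first injection. The last-injection rule is a conflict between the footnote and the Section 7.3.2 text, worth 10 to 18 percentage points in the cases shown. The missing stop at a move to oral, the missing censoring events and the swapped markers are smaller defects in the same table.

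The sizes rest on the illustrative calendars and an uncensored 365-day window. The effect on the reported mean and median cannot be computed, because the documents give neither injection patterns nor switch times.

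A reader might infer that half of the CAB LA group is affected, by taking 767 − 384 = 383 as switchers (383/767 = 50%). The protocol never states 383. On its stated 292 the share is about 38–43%, from counts that do not reconcile. Table 12 covers only 12 months from index, and the share switching within that time is not given. Switchers are a material part of the group, but the exact fraction is unknown.

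Nor do the documents require restarting the 12 months at the first injection. Objective 4 sets the window from index, and the ratio can be repaired inside it.

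**What to change.** Use one definition in Section 7.3.2 and Table 12:

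- **Numerator:** sum over all injections, including the last, of min(37 or 67 days, days to the next injection or to the end of CAB LA follow-up).
- **Denominator, every CAB LA user:** days from the first CAB LA injection to the earliest of 12 months after index, death, loss to follow-up or study end. Add the start of oral PrEP as an end point, for consistency with Table 11; this is a design choice to state openly.
- **Markers:** attach the days-covered footnote to the days-covered rows and the follow-up footnote to the follow-up rows.

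Reconcile 384, 292 and 767 in Section 7.5, and report how many people switched to CAB LA within 12 months of index.

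The cost is wording and programming, with no new data. Coverage figures will change, so any Analysis #1 output already produced from Table 12 as written would need to be rerun.

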7.3.2. Outcome definitions

People without HIV in OPERA (Obj 1)

Incident HIV diagnosis

- New HIV diagnosis and/or detectable HIV RNA and/or positive antigen/antibody test
- All potential incident HIV diagnoses will be subject to a thorough chart review for confirmation

People with a new HIV diagnosis (Obj 1.a)

Not applicable

Protocol for Non-Interventional Studies PASS Studies and Non-PASS Studies (4.0) March 2024

Template Doc ID: TMF-15706807

Parent Doc ID: VQD-SOP-066694

PrEP users (Obj 2-5)

Incident HIV diagnosis

- Frequency of new HIV diagnosis and/or detectable HIV RNA and/or positive antigen/antibody test
- Months from start of PrEP type (oral vs. LA) to HIV diagnosis
- Rate of incident HIV diagnoses per 100 person-years of follow-up
 - Within the first 12 months after index PrEP start
 - Through study end (Analysis #1: 30JUN2024; Analysis #2: 30JUN2025)
 - Follow-up (FU) will be censored at first of:
 - HIV diagnosis
 - Death
 - Study end (Analysis #1: 30JUN2024; Analysis #2: 30JUN2025)
 - Loss to follow-up (12 months after last clinical contact)
 - 12 months after index date
- All potential HIV acquisitions will be subject to a thorough chart review for confirmation
 - All lab results, diagnoses, ART prescriptions and clinician notes available in OPERA on or after the potential HIV acquisition was identified will be reviewed

PrEP coverage

- Oral PrEP coverage:
 - Proportion of days of access to oral PrEP in the 12-months following index PrEP initiation
 - Follow-up (FU) will be censored at first of:
 - a) Death
 - b) Study end (Analysis #1: 30JUN2024; Analysis #2: 30JUN2025)
 - c) Loss to follow-up (12 months after last clinical contact)
 - d) 12 months after index date
 - Access to oral PrEP will be determined based on the dates and days of supply for each prescription (e.g., a prescription for 30 pills/month with 3 refills provides 90 days of access)
 - a) Each calendar day will only be counted once, even if there is an overlap between access from the prior prescription and start of the next prescription.

$$\% \text{ access} = \frac{\sum \text{Number of pills in each prescription}}{\text{Number of FU days}} \times 100\%$$

- LA PrEP coverage:
 - Proportion of days of coverage by CAB LA over follow-up
 - Follow-up (FU) will be censored at first of:
 - a) Death
 - b) Study end (Analysis #1: 30JUN2024; Analysis #2: 30JUN2025)

- c) Loss to follow-up (12 months after last clinical contact)
- d) 12 months after index date

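### The Table 12 footnote and the literal 7.3.2 formula give no CAB LA coverage after the last injection, although the 7.3.2 text credits every injection forward from its date

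*Protocol*

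**What the plan says.** The measure for Objective 4 in Protocol section 7.3.2 is "Proportion of days of coverage by CAB LA over follow-up". The same section gives the rule: "Coverage by LA PrEP will be determined based on the duration of medication from injection date forward". A first injection earns 37 days (30 plus a 7-day window) and each subsequent one 67 days (60 plus 7). Neither credit depends on a later injection taking place. Overlap between successive injections is handled separately: "Each calendar day will only be counted once, even if there is an overlap between coverage from the prior injection and date of the next".

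The formula printed below these rules divides a sum of minima by the number of follow-up days. The two terms inside each minimum are "coverage, days between injections". It does not say what the second term is when no further injection exists.

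Annex 1, Table 12 restates days covered in a footnote: "Total days between injections, up to 37 days between the first 2 injections or up to 67 days between subsequent injections". Its letter is b, which the table rows attach to days of follow-up. The rows for days covered carry letter a, whose text describes follow-up. The two letters are swapped, and by content the quoted note can only belong to days covered.

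Follow-up in 7.3.2 ends at death, study end, loss to follow-up or "12 months after index date". Stopping CAB LA does not end it.

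**The concern.** An interval between injections needs two injections. The last injection a person receives opens an interval that nothing closes, so the footnote, and the formula read literally, give it no days. A person with a single injection scores zero days covered, although the 7.3.2 text gives that person 37. The days after the last injection still count as follow-up, so the percentage falls.

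Relative to the text rule, this error can only lower coverage, and its relative effect is largest in people who stop early. CAB LA coverage is half of Objective 4, which section 6 lists among the primary objectives. Two programmers, one working from the 7.3.2 text and one from the table shell, would report different means and medians from the same records.

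**Working it through.** **Inputs from the protocol (7.3.2):** first injection 30 + 7 = 37 days; subsequent injections 60 + 7 = 67 days; follow-up capped at 12 months. Both credits reproduce. The protocol states no expected coverage percentage, so there is none to check against.

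**Assumptions, because the protocol gives no injection data:** injections on days 0, 30, 90, 150, 210, 270 and 330; follow-up F = 365 days; the person stops after k injections. Let t_i be the day of injection i, with c_1 = 37 and c_i = 67 for later injections.

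- Reading A (footnote, or literal formula): days covered = sum over i = 1 to k−1 of min(c_i, t_(i+1) − t_i).
- Reading B (7.3.2 text, cut at end of follow-up): reading A plus min(c_k, F − t_k).

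| k | A, days | A, % | B, days | B, % | Difference, points |
|---|---|---|---|---|---|
| 1 | 0 | 0 | min(37, 365) = 37 | 10.1 | 10.1 |
| 2 | min(37, 30) = 30 | 8.2 | 30 + 67 = 97 | 26.6 | 18.4 |
| 3 | 30 + 60 = 90 | 24.7 | 90 + 67 = 157 | 43.0 | 18.4 |
| 4 | 30 + 2×60 = 150 | 41.1 | 150 + 67 = 217 | 59.5 | 18.4 |
| 7 | 30 + 5×60 = 330 | 90.4 | 330 + min(67, 35) = 365 | 100 | 9.6 |

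**Bounds.** The difference is min(c_k, F − t_k). It cannot exceed 37 days with one injection (37/365 = 10.1 points) or 67 days with two or more (67/365 = 18.4 points). With shorter follow-up the same days weigh more: one injection and 180 days gives 0% against 37/180 = 20.6%.

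**When the difference vanishes.** If an eighth injection falls on day 365, both readings give 365/365. If an eighth injection on day 390 is used to close the interval and the result is cut at day 365, both again give 365/365.

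**The missing cut at end of follow-up.** Entered into the formula literally, that day-390 injection adds min(67, 60) = 60 days, giving (330 + 60)/365 = 106.8%. Crediting the day-330 injection with an uncut 67 days gives (330 + 67)/365 = 108.8%. The printed formula excludes neither.

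**The case against.** The strongest reply is that 7.3.2 is the outcome definition and Annex 1 only a table shell, and that the 7.3.2 text is sound. It credits every injection forward, and the once-per-day rule shows that the minimum is there to prevent double counting, not to drop the last dose. This stands in part. A reader might infer that the protocol has settled on zero coverage after the last injection, or on 0% for a one-injection user. The documents do not support that: text and footnote contradict each other, and the formula is silent on the last interval.

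A reader might also infer that every CAB LA user loses coverage, or that 10 to 18 points are lost per person. That does not hold either. The loss is near zero when the last injection falls close to the end of follow-up, or when a later injection closes the interval. In Analysis #1, data run to 30JUN2024, 12 months past the last inclusion date, so such later injections may be on record for many people who continue.

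Nor should the results above 100% be taken as the protocol's intended outcome. The measure is a proportion of follow-up days, and days after censoring are not follow-up days. What remains is that neither the formula nor the footnote states the cut.

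Finally, the study is descriptive, and oral access and CAB LA coverage are separate measures in separate tables, with no planned contrast of the two. That limits the consequence, but it does not make the CAB LA figure correct. The objection that such detail belongs in a later analysis specification does not succeed, because the protocol itself fixes a rule, a formula and a footnote that disagree.

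**Conclusion.** The point holds as an internal contradiction with a one-sided effect. If the Table 12 footnote or the literal formula is programmed, CAB LA coverage is understated for people who stop or whose last injection falls well before the end of follow-up. Under the assumed schedule and 365 days, the shortfall is 10.1 points for one injection, 18.4 points for people who stop after two to four, and up to 9.6 points for seven on-schedule injections with no later one counted. If the 7.3.2 text is programmed with a cut at the end of follow-up, there is no understatement.

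The percentages are illustrations. They rest on the assumed injection days and a 365-day denominator, and so describe people whose index regimen is CAB LA with full follow-up. They do not describe people who switch from oral PrEP, whose time on CAB LA differs. The effect on the reported mean or median depends on how many users stop early, which the protocol does not give.

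**What to change.** In the 7.3.2 formula and in the Table 12 note, define days covered as the sum over all CAB LA injections in follow-up, including the last, of

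min(37 for the first injection or 67 for later ones, days to the next injection, days to end of follow-up),

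omitting the middle term when there is no next injection. This keeps the protocol's own day counts, counts each calendar day once and cannot exceed 100%. In the same edit, swap the a and b footnote letters in Table 12 so that each note sits under the row it describes.

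The cost is one formula line and one footnote in the protocol, with the matching program line. No new data are needed.
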